number of PLWH participants in Stage 1A will be n=32. Additionally, we will conduct 4 FGDs with health workers at our study clinics. These FGDs will also have a maximum number of 8 participants per group, thus the maximum number of healthcare worker participants will be n=32. Finally, we will conduct up to 16 key informant interviews with policy officials and relevant program leaders.

Stage 1B: This stage will enroll n=320 participant who have hazardous alcohol use: n=160 will formally be enrolled in the RCT (participants who meet criteria for a moderate-to-severe AUD or have hazardous alcohol use plus comorbidities) and n=160 who will not be enrolled in the RCT but will receive the BI and will be tracked for follow-up in a cohort study (participants with hazardous use but do not have a moderate-to-severe AUD and have no comorbidities).

The primary endpoint of the pilot RCT is the difference in change in AUDIT score from baseline to 6-month follow-up between BI+CETA and BI alone (see assessments section below). We believe that an effect size of CETA  $\geq 0.5$  would be clinically significant and justify further investigation in a subsequent latter Stage trial. Further assuming  $\alpha=0.05$  and  $\beta=80\%$ , we will require a total sample size of 128 (n=64 per arm). To account for possible loss-to-follow-up/drop-out of 20% based on our previous studies with HIV-affected populations in Zambia, we will inflate the sample size to 160 (n=80 per arm). Based on Preliminary Studies, we anticipate that 20% of female and 40% of male patients at the study sites will report hazardous drinking and that 50% of hazardous drinkers will qualify for the RCT. Therefore, we expect to enroll n=320 hazardous drinkers to reach the RCT target sample size. There is no sample size calculation for cohort study participant; however, the anticipated sample of n=160 should be sufficient to detect even a small within-group change in outcomes after receipt of BI.

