1. Screening for eligibility into the overall study. Participants will provide informed consent for the screening activity. They will then complete a screener that consists of demographic information and the Alcohol Use Disorders Identification Test administered via the audio computer assisted self-interviewing (ACASI). Eligibility criteria for this stage are:

- HIV positive
- Receiving HIV treatment services at one of the two study clinics
- Current hazardous alcohol use, defined as an AUDIT score of  $\geq 8$  for men and  $\geq 4$  for women

Following the ACASI screener, the ACASI system will alert the assessor if the participant is eligible or not. If not eligible, the participant will exit the study. If eligible, the participant will conduct the secondary screening to determine whether they will be part of the cohort or the RCT. The additional screening questions will also be administered via ACASI. Participants will be enrolled into the cohort study unless one or more of the following conditions are met:

- AUDIT scores that indicate a moderate-to-severe AUD ( $\geq 12$  for women;  $\geq 16$  among men)
- AND/OR: meeting validated symptom criteria for depression ( $\geq 16$  on CES-D), trauma/anxiety ( $\geq 2.5$  on HTQ), and/or substance use ( $\geq 27$  for any non-tobacco/alcohol substance on ASSIST)

If any of these conditions are met, the participant will be eligible for and enrolled into the RCT.

Cohort study participants (i.e., lower risk participants) will not be randomized. They will receive the brief alcohol intervention and we will conduct a 6 month post-baseline assessment. The purpose of including them in the study is to gain some preliminary data on whether the brief intervention may be helpful in reducing alcohol consumption among these participants that have a lower level alcohol use problem and no significant mental health or other substance use comorbidities. They are not formally included in the RCT because we did not have the resources to do so in this pilot grant.

RCT participants (i.e., higher risk participants) will be randomized to receive either the brief intervention alone or the brief intervention + CETA. Similar to the cohort participants, we will conduct a 6 month post-baseline assessment among all RCT participants. The purpose of the RCT is to assess whether the BI

alone is effective or whether a more substantial intervention (BI +CETA) is necessary for these higher risk participants.

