### Stage 1B: Piloting of CETA referral and treatment in HIV clinics.

[figure not shown]
Stage 1B of the study will be a pilot RCT of CETA delivery in HIV clinics. Our hypothesis is that BI+CETA will be more effective than BI alone at treating severe AUD, mental health, and substance use problems. As such, the two populations targeted for this pilot RCT are those that are 'higher risk', namely: (1) PLWH with hazardous drinking and comorbidities; and (2) PLWH with moderate-to-severe AUD (with or without comorbidities). BI alone is currently the standard of care and only alcohol treatment in Zambia HIV clinics and therefore an appropriate comparison to BI+CETA. Participants in these two groups will be randomized 1:1, stratified by sex, to receive BI+CETA or BI alone. Alcohol, substance use, and mental health outcomes will be assessed at baseline and 6-months post-baseline. Retention on ART and HIV viral suppression will also be assessed at baseline and 6-months post-baseline. These HIV outcomes will be assessed as part of usual HIV care. We will also systematically capture data on intervention uptake, attendance, and completion, clinical monitoring, and implementation factors.

Although our focus is on the feasibility of delivering a higher intensity and potentially more effective therapy (i.e., CETA) for individuals at higher risk, we will also provide BI alone for PLWH who report hazardous alcohol use *without* comorbidities and do not meet criteria for a moderate-to-severe AUD (individuals at 'lower risk', referred to as 'cohort' participants in the consent form) and evaluate their outcomes to lay broad foundation for a stepped care intervention in the future. That is, in a real-world program, these are PLWH who would be initially targeted by BI alone. Although enrolling these participants into an RCT is beyond the scope of this study, we will collect pre/post data on the same outcomes as the pilot RCT participants to estimate within group effects of the BI alone for these lower risk drinking problems.

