Study Phase	Activity	Year 1				Year 2				Year 3			
		Q 1	Q 2	Q 3	Q 4	Q 1	Q 2	Q 3	Q 4	Q 1	Q 2	Q 3	Q 4
Planning	Study protocol finalization and ethical approval												
	Staff hiring and site preparation												
	Training of qualitative data staff												
Stage 1A	Focus groups and key informant interviews												
	Adaptation of CETA for PLWH												
	Development of CETA protocol in HIV care based on Stage 1A												
	CETA/mhGAP-IG trainings, assessor trainings, M&E trainings												
Stage 1B	CETA pilot cases												
	Recruitment, consent, screening and baseline assessments (ACASI, HIV)												
	Interventions active												
	Post-treatment assessments (ACASI, UEtG)												
	6-month outcomes assessment (ACASI, UEtG, HIV outcomes via chart review)												
Analysis, dissemination, and next steps	Implementation data collection (PLWH, clinic staff, policy officials)												
	Data analysis												
	Report/manuscript writing and dissemination at conferences												
	Preparation and submission of follow-up R01												

- Provide a brief data analysis plan and a description of variables to be derived.

*Analysis of treatment uptake and completion.* We will estimate a logit model with a binary outcome (1=completer; 0=non-completer) to assess predictors of treatment completion. Predictors will be demographic (e.g., sex, age), clinical (e.g., symptom severity), and structural (e.g., distance from clinic) level factors.

*Analysis of ACASI outcome data.* Analyses will be intent-to-treat. AUDIT score, along with other continuous secondary outcomes (Past 30-Day TLFB [% days drinking and mean drinks per day], CES-D, HTQ, ASSIST scores) will be modelled with linear mixed models. Fixed effects will include treatment arm (0=BI; 1=BI+CETA), time (0=Baseline; 1=6-months post-baseline), and interaction terms between treatment arm

and time. This will allow estimation of the mean difference in change in score between arms and 95% confidence intervals. Cohen's D will be calculated to estimate effect size. Covariates will be included if they differ meaningfully at baseline or predict significant change in the outcome. For dichotomous outcomes or non-normally distributed continuous outcomes, generalized linear mixed effects models will be estimated. Paired t-tests will be used to assess within group change among the non-Pilot RCT hazardous drinkers.

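### The cohort's paired t-test uses only participants with a 6-month value; a time-only likelihood model with unstructured covariance would use every baseline and remove bias from baseline-related loss

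*Combined protocol and SAP*

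**What the plan says.** Section V, data analysis plan, under Analysis of ACASI outcome data, opens with "Analyses will be intent-to-treat" and names no population. It then specifies linear mixed models for AUDIT and the other continuous outcomes: "Fixed effects will include treatment arm (0=BI; 1=BI+CETA), time (0=Baseline; 1=6-months post-baseline), and interaction terms between treatment arm" and time. Random effects and covariance structure are not stated. The paragraph closes with the cohort: "Paired t-tests will be used to assess within group change among the non-Pilot RCT hazardous drinkers".

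The eligibility text in Section V.B states that "Cohort study participants (i.e., lower risk participants) will not be randomized". The Stage 1B description says the cohort's pre/post data serve to "estimate within group effects of the BI alone for these lower risk drinking problems", as groundwork for stepped care. Outcomes are measured at baseline and 6 months only.

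In Section III.B the 20% allowance belongs to the RCT: "To account for possible loss-to-follow-up/drop-out of 20% based on our previous studies", taking 128 up to 160. For the cohort, "There is no sample size calculation for cohort study participant", but the anticipated 160 "should be sufficient to detect even a small within-group change in outcomes after receipt of BI".

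**The concern.** With one follow-up visit, a single missed assessment removes a cohort member from the paired t-test. There is no comparator, so the mean change is the whole result and selective loss enters it directly. The completers' mean change equals that of everyone enrolled only if loss is unrelated to the expected change. A likelihood model with a suitable covariance needs less: loss may depend on the observed baseline.

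Baseline-related loss is plausible on the protocol's own rationale. Section II links hazardous drinking to poorer retention in HIV care, and Section V tries to align the 6-month assessment with a routine HIV visit. At stake is the accuracy of the brief-intervention estimate meant to inform a later stepped-care study.

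**Working it through.** **The plan's own figure.** The RCT size reproduces. For d = 0.5, two-sided alpha 0.05 and 80% power, the two-sample t calculation gives 63.77, so 64 per arm and 128 in total; 128 / 0.8 = 160. The cohort has no figure to reproduce.

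**Inputs.** From the documents: cohort n = 160; two time points; cohort AUDIT bands of 8-15 for men and 4-11 for women, from the entry and RCT thresholds in Section IV. Assumed: 20% loss in the cohort, so 160 x 0.8 = 128 pairs remain; correlation r of 0.3, 0.5 or 0.7; ratio k of 6-month to baseline SD of 1, 1.5 or 2; and a gap g, in baseline SD, between the mean baseline of those lost and those kept.

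**Formula.** When loss depends on baseline only, the completers' baseline mean is too low by loss x g, and expected change has slope (r x k - 1) on baseline. Hence

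bias of paired mean change = loss x g x (1 - r x k).

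A positive value means a fall is understated when heavier drinkers are lost.

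**Equal SDs (k = 1), r = 0.3 / 0.5 / 0.7.**
- g = 0.48: 0.2 x 0.48 x (0.7 / 0.5 / 0.3) = 0.067 / 0.048 / 0.029 SD.
- g = 0.86: 0.2 x 0.86 x (0.7 / 0.5 / 0.3) = 0.120 / 0.086 / 0.052 SD. Simulations put the largest of these at 0.12 to 0.13.
- Standard error = sqrt(2(1 - r)/128) = 0.105 / 0.088 / 0.068. The bias is therefore about 0.4 to 0.6 standard errors for the smaller gap and 0.8 to 1.1 for the larger.
- Simulated coverage of the paired 95% interval was 91-93% for the smaller gap and 78-89% for the larger.

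**What the model does.** With unstructured covariance and loss only at the second visit, the estimated 6-month mean is the completers' 6-month mean plus b x (baseline mean of all - baseline mean of completers), where b is the completers' regression slope. Simulated bias in baseline SD (n = 160, 20% loss, log-odds of loss 1 per baseline SD, 2,000 runs each), at r = 0.3 / 0.5 / 0.7:

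| k | Paired t-test | Unstructured | Random intercept only |
|---|---|---|---|
| 1 | +0.12 / +0.09 / +0.05 | about 0 | about 0 |
| 1.5 | +0.10 / +0.04 / -0.01 | about 0 | -0.03 / -0.06 / -0.07 |
| 2 | +0.07 / 0.00 / -0.07 | about 0 | -0.07 / -0.11 / -0.15 |

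The unstructured estimate stayed within 0.005 throughout. A random intercept alone forces equal variances. It was worse than the paired t-test at two of three correlations for k = 1.5; for k = 2 it was about equal at r = 0.3 and worse at the other two. The baseline-only records must also be included: on one simulated data set, a random-intercept model fitted to completers alone returned the paired t-test result (-0.2086, SE 0.0804).

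**Other loss mechanisms, k = 1.**
- Completely random loss: no bias in any method, and little precision gained (SE 0.106 against 0.101 at r = 0.3).
- Loss depending on the 6-month value: paired -0.12 / -0.09 / -0.05; unstructured -0.16 / -0.13 / -0.09.

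**In AUDIT points.** If scores were spread evenly over the two bands with equal numbers of each sex (an assumption), the within-sex variance is (8^2 - 1)/12 = 5.25. The means 11.5 and 7.5 add 2^2 = 4, so the SD is sqrt(9.25) = 3.04. Then 0.03 to 0.13 SD is about 0.1 to 0.4 points.

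**The case against.** A reader might infer that the paired t-test breaches the plan's intent-to-treat statement. The documents do not support that. Intent-to-treat concerns analysis by randomized allocation, and the cohort is one unrandomized group, all offered the same intervention. The statement also introduces a model whose arm term the cohort does not have. What remains is missing data left unaddressed in the cohort, beside a sentence that does not say whom it covers.

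A reader might also infer that the RCT's mixed model, carried over, would remove the bias. It cannot be carried over unchanged because it has arm terms, and its covariance is unstated. Eligibility truncates the cohort's baseline AUDIT but not the 6-month score, so a larger 6-month SD is plausible, and a random-intercept version could then do harm. This objection stands and shapes the fix. It does not defeat the unstructured version: with a bounded eight-point baseline and k = 1.5, its simulated bias was at most 0.004 and its coverage 95-96%.

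Three further objections stand. The 20% is not a plan figure for the cohort. The direction of bias is not fixed: it reverses once r x k exceeds 1. Neither method cures loss that depends on the 6-month outcome.

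Finally, the stakes are small: a paired t-test is a common choice for preliminary, uncontrolled pre/post data, and the effect is a fraction of an AUDIT point.

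**Conclusion.** The point holds as a minor improvement. The planned cohort analysis uses completers only, and a better method needs no new data. With an assumed 20% loss that depends on baseline, the completer estimate is off by about 0.03 to 0.13 baseline SD at equal SDs and correlations of 0.3 to 0.7. With a larger 6-month SD the error can shrink to nothing or change sign. The unstructured model is close to unbiased in all these cases at essentially the same standard error.

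That advantage rests on loss depending only on the observed baseline. It disappears under completely random loss, and at equal SDs it reverses slightly if loss depends on the 6-month value. The plan is not shown to breach intent-to-treat, and the RCT primary endpoint is unaffected.

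**What to change.** Replace the cohort sentence in the data analysis plan with the following content:
- Cohort change will be estimated by a likelihood-based repeated-measures model with time (baseline, 6 months) as the only fixed effect and an unstructured 2x2 covariance, not a random intercept alone.
- Every cohort member with a baseline value will be included.
- Mean change will be reported with its 95% CI.
- The paired t-test will be kept as a completer sensitivity analysis.
- Baseline values will be tabulated by 6-month follow-up status.

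It would also help to say whether the intent-to-treat sentence covers only the RCT. The cost is a few lines of text and a little more analysis, with no new data or visits. The plan should acknowledge that the model does not correct loss that depends on the 6-month outcome and may be slightly more biased than the paired t-test in that case.

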### Stage 1B:

Study participants will be PLWH who are currently receiving care at one of the two study clinics. Participants will be recruited by their regular care providers (i.e., peer educators, counselors, nurses, physicians) and referred to study staff if they are interested. We anticipate enrolling a total of 320 participants, all of whom have hazardous alcohol use. 50% of them will be lower-risk drinkers who do not have moderate-to-severe alcohol use disorders (AUD) or mental health comorbidity. These participants will be part of the 'Cohort Study'. These will not be randomized. The other 50% will be high-risk drinks due to having either moderate-to-severe AUD or mental health comorbidities, or both. This second group will be randomized into the RCT Study. The minimum age of research subjects will be 18. All subjects will be recruited from our two study clinics. Eligibility will be assessed via audio computer assisted self-interviewing (ACASI).

*Initial* inclusion criteria for overall enrollment (into either the Cohort or RCT study) will be:

- HIV positive
- Receiving HIV treatment services at one of the two study clinics
- Current hazardous alcohol use, defined as an AUDIT score of  $\geq 8$  for men and  $\geq 4$  for women
- Provides informed consent

*Secondary* inclusion for enrollment into the RCT will be:

- AUDIT scores that indicate a moderate-to-severe AUD ( $\geq 12$  for women;  $\geq 16$  among men)
- AND/OR: meeting validated symptom criteria for depression ( $\geq 16$  on CES-D), trauma/anxiety ( $\geq 2.5$  on HTQ), and/or substance use ( $\geq 27$  for any non-tobacco/alcohol substance on ASSIST)

Participants who meet initial inclusion criteria AND secondary inclusion criteria will be eligible for the RCT. Participants who meet initial inclusion criteria but NOT secondary inclusion criteria will be eligible for the Cohort study.

- **Exclusion Criteria:**

Stage 1A: No formal exclusion criteria.

Stage 1B: Study exclusion criteria for Stage 1B (applies to the Cohort study and the RCT) will be:

- HIV negative

- Not receiving care at one of the study clinics
- Currently psychotic or on an unstable psychiatric drug regimen
- Actively suicidal: Suicide attempt or suicidal ideation with intent or plan, or self-harm in the past month.
- Unable to provide informed consent

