Baseline data collection. The baseline assessment will be conducted via ACASI. The participant will first complete the Alcohol Use Disorders Identification Test (AUDIT) to assess eligibility into the study. The ACASI will automatically alert the assessor if the participant is eligible based on the hazardous alcohol use criteria. If eligible, the participant will complete the remaining measures: (1) Center for Epidemiological Studies-Depression Scale (CES-D); (2) Harvard Trauma Questionnaire (HTQ); and (3) the Alcohol, Smoking, and Substance Involvement Screening Test (ASSIST). All of these measures have previously been translated and used by our team in Zambia and the AUDIT, CES-D, and ASSIST measures have been formally validated. A research assistant will be available if there are any challenges with the ACASI. Additionally, we will use HIV clinic files to extract HIV-related data. These data are captured as part of HIV routine care in Zambia and include: (1) ART initiation date, (2) hepatitis B surface antigen, (3) most recent CD4+ count, (4) cumulative and past 6-month ART retention, defined by medication possession ratio (MPR; an objective pharmacy record metric that we have used previously) and (5) plasma HIV viral load (measured at CIDRZ Central laboratory using the Roche COBAS/Ampliprep platform).

Secondary eligibility criteria for the RCT. Following completion of the baseline assessment, ACASI will automatically alert the assessor if the participant is eligible for the pilot RCT via a built-in algorithm. Criteria for the RCT will be (a) AUDIT scores that indicate a moderate-to-severe AUD ( $\geq 12$  for women;  $\geq 16$  among men) and/or (b) meeting validated symptom criteria for depression ( $\geq 16$  on CES-D), trauma/anxiety ( $\geq 2.5$  on HTQ), and/or substance use ( $\geq 27$  for any non-tobacco substance on ASSIST).

Randomization. Participants eligible for the pilot RCT will be randomized 1:1, stratified by sex, to receive the BI alone or BI+CETA. Participants who are NOT eligible for the pilot RCT will be provided with a BI but will not be randomized.

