Follow-up assessments. Alcohol and comorbidities will be assessed in all participants at 6 months (i.e., endline) after baseline. The ACASI questionnaire that was used at baseline will again be administered at this follow-up visit (i.e., the questionnaire at this visit is the same as at baseline). In addition to ACASI assessments, we will confirm self-reports of alcohol abstinence on the AUDIT by conducting a urine-based rapid alcohol biomarker test, ethyl glucuronide (uEtG). Finally, at the 6-month post-assessment, which coincides with a regularly scheduled clinic visit, we will extract relevant information from the client's HIV clinical record (this will be the same information that is collected at baseline), including: , (1) hepatitis B surface antigen, (2) most recent CD4+ count, (4) cumulative and past 6-month ART retention, defined by medication possession ratio (MPR; an objective pharmacy record metric that we have used previously) and (4) plasma HIV viral load (measured at CIDRZ Central laboratory using the Roche COBAS/Ampliprep platform). We will not collect any additional biospecimens for purposes of the study—all HIV-related data will be captured via chart extraction. To supplement retention data captured through MPR measurement, we will also assess visit adherence, the percentage of assigned pharmacy and clinical visits that were made (coming to clinic within 3 days).

Implementation data collection. We will conduct a mixed methods process evaluation with stakeholders involved in the CETA referral and treatment process, including follow-up FGDs and KIIs with participants from Stage 1A and CETA counselors. We will also conduct mixed methods interviews with approximately N=30 PLWH who participated in the Stage 1B pilot RCT. This will include a purposeful sample of PLWH from a range of ages and both sexes who did and did not complete the BI and CETA. Implementation factors to be explored will include: acceptability, appropriateness, reach, cost, feasibility, and sustainability and will explore the attitudes, thoughts, feelings, and barriers and facilitators related to implementation. Interviews will include an in-depth interview component and JHU quantitative implementation measures.

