Data management. All uptake/completion, clinical monitoring, HIV outcome, and uEtG data will be double entered into password protected databases by research staff weekly. ACASI data will be electronically transferred from field laptops at the HIV clinics into the study database at CIDRZ headquarters daily. De-identified data will be transferred to JHU weekly. [name] will run data checks and return queries for resolution. [name] and [name] will hold weekly calls with the Zambian data team.

- Describe the number and type of study visits and/or contacts between the study team and the participant, how long they will last, and where/how they will take place.

Stage 1A: We expect to have two study visits with focus group participants (PLWH and healthcare workers). The first visit will be the recruitment/consent visit. The second visit will be the actual focus group session. The first visit we expect to take approximately 30 minutes. We expect the focus groups to be between 60-90 minutes. We expect to have one study visit for key informants in which we will conduct both the consent and interview. We expect these sessions to be approximately 60-90 minutes. A third contact may be conducted with some of the healthcare workers and key informants at the end of the study to discuss implementation factors in an in-depth interview or focus group. This third visit will be approximately 60-90 minutes in length.

Stage 1B: Participants in the pilot will have an initial study visit for consent/screening/baseline/BI. The initial visit, which includes informed consent and baseline ACASI to capture data, may take up to 120 minutes. If they are randomized to CETA they will have an additional 6-12 weekly therapy sessions (approximately 60 minutes each). All participants will have a post-assessment visit approximately again 6 months post-baseline (we will attempt to have the 6 month assessment align with a regular HIV care visit). The follow-up study assessments we expect to take approximately 45 minutes. We will also ask a sample of participants to participate in a mixed methods interview following the study on implementation outcomes.

- Describe the expected duration of the study from the perspective of the individual participant and duration overall.

From the perspective of participants, the study will be approximately 6 months. Overall, we expect the study to take 3 years, including final data analysis. An estimated timeline is provided below.

**Table 4.** Study timeline

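### The cohort's AUDIT change is measured from the score that selected its members, so a paired test against zero cannot show whether the brief intervention works

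*Combined protocol and SAP*

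**What the plan says.** All references are to the combined protocol and SAP.

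- **Selection.** Section IV (Stage 1B) sets the entry condition: "Current hazardous alcohol use, defined as an AUDIT score of" 8 or more for men and 4 or more for women. People at 16 or more (men) or 12 or more (women), or above a cut on CES-D, HTQ or ASSIST, go to the RCT. The cohort is therefore the AUDIT window 8-15 (men) or 4-11 (women), with all three comorbidity scales below their cuts.
- **Baseline.** Section V, Baseline data collection: "The participant will first complete the Alcohol Use Disorders Identification Test (AUDIT) to assess eligibility into the study". The visit description adds: "Participants in the pilot will have an initial study visit for consent/screening/baseline/BI". There is no second AUDIT before the BI.
- **Follow-up.** At 6 months, "the questionnaire at this visit is the same as at baseline".
- **Analysis.** Under Analysis of ACASI outcome data: "Paired t-tests will be used to assess within group change among the non-Pilot RCT hazardous drinkers". There is no untreated comparator.
- **Interpretation.** The Stage 1B overview says the cohort data will "estimate within group effects of the BI alone for these lower risk drinking problems". The screening section is softer: "preliminary data on whether the brief intervention may be helpful in reducing alcohol consumption".
- **RCT purpose.** In the screening section, the sentence beginning "The purpose of the RCT is to assess whether the BI" goes on to ask whether BI alone is effective or the fuller package is needed, although both arms receive the BI.

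Regression to the mean is not mentioned anywhere.

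**The concern.** A score chosen for lying inside a window is partly true level and partly transient variation. When it is measured again, the group mean moves back toward the mean of the population it was drawn from, whether or not anything was done in between. A paired t-test takes zero change as its null, but here the no-effect value is the regression drift.

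The cohort is meant to inform BI as the first step of a stepped-care programme. A significant fall could be read as evidence that BI works when it does not. If the drift is upward, a real benefit could be missed. Section III.B presents the cohort as large enough to detect even a small change, and that sensitivity extends equally to a small artefact.

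**Working it through.** **The plan's own figure.** The cohort has no sample size calculation; the RCT does. For d = 0.5, two-sided alpha 0.05 and 80% power: 2(1.96 + 0.84)²/0.5² = 62.7, so 63 per arm by the normal formula and 64 by the exact t-test. Then 128/0.8 = 160, and 160/0.5 = 320 hazardous drinkers. The figures reproduce.

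**Sensitivity of the paired test.** The standardised change detectable with 80% power is 2.80/√n: 2.80/√160 = 0.22, and 2.80/√128 = 0.25. The 128 applies the RCT's 20% loss to the cohort, which is an assumption.

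**Expected change with no BI effect.** If scores at the two visits share one distribution with mean μ and correlation r, and regression is linear:

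expected change = −(1 − r) × (mean score inside the window − μ)

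For a normal distribution, the bracket is σ[φ(a) − φ(b)]/[Φ(b) − Φ(a)], where a and b are the standardised window limits.

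*From the documents:* the windows, and 40% of men and 20% of women above the lower cut (Section III.B). *Assumed:* the shape of the distribution, the 6-month correlation r, and q, the share of hazardous drinkers above the upper AUDIT cut. None of the models conditions on the comorbidity scales.

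**Normal model.** Men with mean 6 and SD 6 have 40% at 8 or above. With limits 7.5 and 15.5, a = 0.25 and b = 1.583, so the bracket is 6 × (0.387 − 0.114)/0.345 = 4.75. The expected change is −0.3 × 4.75 = −1.42 at r = 0.7 and −0.1 × 4.75 = −0.47 at r = 0.9. Women need mean 0.15 and SD 4 to give 20% at 4 or above. Simulating both sexes with scores rounded and held to 0-40, AUDIT falls by 0.5 to 1.5 points, and the paired test at n = 128 is significant in 67% to 99% of trials (r from 0.9 to 0.7). This model is implausible for women: it centres them at the scale floor and puts only about 1% of hazardous women at 12 or above, so almost no upper tail offsets the fall.

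**Skewed model** (integer scores 0-40, same 40% and 20%, n = 128):

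| q | r | change, men / women | significant fall | significant rise |
|---|---|---|---|---|
| 0.30 | 0.5 | −1.30 / −1.74 | 64% | 0% |
| 0.30 | 0.7 | −0.72 / −0.81 | 31% | 0.1% |
| 0.30 | 0.8 | −0.43 / −0.53 | 19% | 0.2% |
| 0.30 | 0.9 | −0.21 / −0.26 | 10% | 0.3% |
| 0.45 | 0.5 | −0.53 / −0.73 | 14% | 0.3% |
| 0.45 | 0.7 | −0.06 / +0.17 | 3% | 1.5% |
| 0.45 | 0.8 | +0.08 / +0.44 | 2% | 3.3% |
| 0.45 | 0.9 | +0.07 / +0.39 | 2% | 2.7% |

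A separate run gives falls in 11% to 62% (q = 0.30) and 1% to 13% (q = 0.45), within a few points of the table. The nominal rate in each direction is 2.5%.

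**Provider pre-selection.** Section V.A has care providers pick out patients they expect to qualify, but does not say how strongly this filters. Suppose 80% of those screened exceed the lower cut. In the normal model with q = 0.45, men have mean 13.1 and SD 6.7, the bracket is 6.7 × (0.281 − 0.374)/0.438 = −1.42, and at r = 0.5 the expected change is +0.71. In the skewed model, significant rises occur in 11% to 93% of trials at n = 160 (q = 0.30 to 0.45, r = 0.9 to 0.5).

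**Comorbidity scales.** CES-D, HTQ and ASSIST are selected low, so they tend to drift upward. For a normal score with a share p below the cut, the drift in SD units is (1 − r)φ(z)/p, where z is the cut's standard normal value. At p = 0.8 and r = 0.9 it is 0.1 × 0.280/0.8 = 0.035; at p = 0.5 and r = 0.5 it is 0.5 × 0.399/0.5 = 0.40. Both p and r are assumed.

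**The case against.** The best defence is that the plan claims little. The analysis sentence speaks of within-group change, Section III.B speaks of change after receipt of BI, the screening section calls the data preliminary, non-randomisation is explained by resources, and testing of stepped care is left to a larger study. That is fair, and it limits the seriousness. It does not remove the point: the Stage 1B overview still calls the change an effect of BI alone, and no caveat tells a reader that zero is the wrong reference.

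The second defence is that the window is cut on both sides, so the two ends partly cancel. This also stands. With 45% of hazardous drinkers above the upper cut and r of at least 0.7, significant falls are near the nominal rate even without provider pre-selection.

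A reader might therefore infer too much in three ways:

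- **That an ineffective BI will look effective, or that near-nominal error is confined to the most favourable case.** The documents do not support this. They give neither the AUDIT distribution of those screened nor the 6-month correlation. The prevalences of 40% and 20% describe clinic patients, not those referred for screening.
- **That the RCT is affected.** It is not: both arms are selected alike, so the drift is common to both and the difference in change between arms does not inherit it.
- **That the RCT is designed to prove BI alone effective.** The RCT-purpose sentence is loosely worded, but Hypothesis 1 and the primary endpoint are purely between-arm, so this is a secondary wording matter.

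**Conclusion.** The concern holds as a matter of interpretation. The selecting AUDIT is the baseline, there is no comparator, and the change is labelled an effect of BI. Rejecting zero change would therefore not show that BI works, and failing to reject would not show that it does not.

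The magnitude cannot be pinned down. With no BI effect, the documents' prevalences and n = 128, the probability of a significant fall runs from about 1% to 99%: 67-99% under the normal model (r 0.7 to 0.9), 11-62% under the skewed model with 30% of hazardous drinkers above the upper cut, and 1-13% with 45% above it (both r 0.5 to 0.9). Little weight should go to the top of that range. Strong pre-selection can remove or reverse the drift. The plan should be changed because the bias is unknown in both size and sign, not because any one figure is established. This is a secondary analysis in a pilot.

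**What to change.** 1. **Analysis of ACASI outcome data (Section V).** Report the cohort's mean change with a 95% CI as descriptive. State that an interval or test excluding zero will not be taken as evidence that BI works. Note that AUDIT may drift either way and that CES-D, HTQ and ASSIST would tend to drift upward.
2. **Sensitivity analysis.** Beside the observed AUDIT change, show the change expected from regression to the mean alone, by sex, with the same two-sided window, using the screening AUDIT distribution and a range of 6-month correlations, for example 0.5 to 0.9. This needs the scores of people screened but ineligible. The plan says they exit the study and does not say whether their scores are kept, so the sponsor should confirm it. Because the correlation is assumed, observed minus expected change should not become the basis for a conclusion.
3. **Stage 1B overview.** Describe the cohort estimate as *within-group change after BI* in place of the wording about effects of BI alone.
4. **Screening section.** State the RCT purpose as BI+CETA versus BI alone.

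The cost is wording, a short calculation that depends on an assumed correlation, and a more modest cohort claim. No visit, participant or intervention changes.
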